### 6.2.2 Descriptive analyses

The variables will be listed by treatment group, patient and visit/time. Summary statistics will be provided for raw, change from baseline and percentage change from baseline by treatment group and visit/time. Summary statistics will include mean (arithmetic), SD, CV, median, minimum, maximum.

Graphical methods will be employed to show group and individual summary plots over time by treatment. Other secondary efficacy variables will be summarized graphically and in summary tables.

### 6.2.3 Statistical model, assumptions and hypotheses

#### HbA1c

The secondary analysis of HbA1c will be analyzed using a mixed effects model with the same structure as the analysis of the primary variable, in Section 6.1.3.

Company Confidential Information

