4.1 Inclusion criteria

1. Written informed consent must be obtained before any assessment is performed.
2. Male and female, age 18 to 75 years (inclusive), in stable health condition as determined by past medical history, physical examination, vital signs, electrocardiogram, and laboratory tests at screening.
3. Type 2 diabetes, with an HbA1c between 6.5% and 10% (inclusive) at screening.
4. On one of the following anti-diabetes regimens with stable treatment for approximately 3 months prior to randomization: 1) metformin monotherapy; 2) DPP4 inhibitor agent monotherapy; 3) combination therapy of metformin and DPP4 inhibitor agent; 4) no anti-diabetes therapy.
5. Body mass index (BMI) of 28.0 to 40.0 kg/m² (inclusive) at screening.
6. Body weight between 65 and 140 kg (inclusive) at screening, and with a stable body weight (± 5 kg) by history (patient report) and stable physical activity within 3 months prior to screening by history (patient report).
7. Able to communicate well with the investigator; to understand and comply with the requirements of the study.

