6.5 Treatment assignment and randomization

Treatment is assigned by stratified randomization for two strata based on the patient's baseline BMI. The strata have the following randomization numbers:

- BMI between 28.0 kg/m² and 33.0 kg/m² (inclusive): 5101 – 5150
- BMI between 33.1 kg/m² and up to 40.0 kg/m² (inclusive): 5201 – 5250

The randomization number is used to identify which strata the patient belonged to at randomization and which treatment the patients have been randomized to receive.

The Patient number assigned to a patient at screening remains the unique identifier for the patient throughout the study. For information on patient numbering, please see 'Subject numbering' section in the SOM.

The randomization numbers will be generated using the following procedure to ensure that treatment assignment is unbiased and concealed from subjects and investigator staff. A randomization list will be produced by, or under the responsibility of, Novartis Drug Supply Management using a validated system that automates the random assignment of treatment arms to randomization numbers in the specified ratio.

BMI was selected as a stratification parameter as it is an important predictor of response on parameters of body composition/body weight and HbA1c (internal data). The expected median value for BMI in this patient population is 33 kg/m² (internal data); therefore, 2 strata above and below/inclusive of the median will ensure a balanced representation of patients between placebo and active drug in each strata, i.e. strata of approximately similar size between the 2 arms. Equal size strata will not be enforced, but a minimal size of 10 will be required for the smaller stratum in order to ensure adequate precision of treatment effect estimation in both strata.

The randomization scheme for patients will be reviewed and approved by a member of the Randomization Office.

Follow the details outlined in the Site Operations Manual regarding the process and timing of treatment assignment and randomization of subjects.

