11.4.2 Statistical model, hypothesis, and method of analysis

The study design enables evaluation of efficacy based on the following dual criteria 1) statistical significance (superior treatment effect, 1-sided 10% level) in fat mass; and 2) clinical relevance of the change in fat mass (estimated median treatment effect of 5% or more). Weight loss of 5% has been shown to translate into clinical benefit in an overweight/obese population with T2D (Franz et al 2015). Fat mass loss of a similar magnitude to the weight loss is expected to translate into similar clinical benefits (such as on glycemic control) in a similar population.

The randomization will be stratified by BMI category (≥ 28.0 kg/m² and ≤ 33.0 kg/m², >33.1 kg/m² to ≤ 40.0 kg/m²) in order to achieve an approximate balance of BMI distribution across the two treatment groups. The cutoff value of 33 kg/m² represents the expected median BMI in that population (based on internal data); therefore the two randomization strata are expected to be of similar size. However, equal size strata will not be enforced. A minimum of 10 patients will be targeted for enrollment in the smaller stratum to ensure accurate precision on the treatment effect in both strata (see Section 11.7).

The primary endpoint will be analyzed using a mixed effects model. This model will have change from baseline in kg fat mass as the dependent variable, treatment arm, time, time*treatment interaction as fixed effects, and a subject level random intercept. Baseline fat mass and baseline BMI value may be included in the model as covariates. Data collected from both randomization strata (BMI category at randomization) will be included in the model. The change from baseline (absolute) in kg fat mass at Week 48 will be estimated from that model and will be summarized graphically and in tabular form. No transformation (logarithmic or otherwise) of body weight will be done for analysis. An unstructured within-subject covariance will be used.

The evaluation of efficacy is based on the following dual criteria:

1. statistical significance (superior treatment effect, 1-sided 10% level) in fat mass; and
2. clinical relevance of the change in fat mass (estimated median treatment effect of 5% or more) at Week 48.

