11.8 Power for analysis of key secondary variables

The power to pass the criteria for HbA1c (significant reduction and an estimated median placebo-adjusted reduction of at least 0.5%) is about 73%. Assumptions used for these calculations include a true placebo-adjusted HbA1c reduction of 0.7% (standard deviation 1.11%, internal data). The associated type I error is about 6%.

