#### 6.1.3 Statistical model, assumptions and hypotheses

The primary analysis will be analyzed using a longitudinal mixed effects model. This model will have change from baseline in kg fat mass as the dependent variable, treatment arm, time, and a time\*treatment interaction as fixed effects. Baseline fat mass and baseline BMI value may

be included in the model as covariates. Time will be modeled as a categorical variable. An unstructured within-subject covariance will be used.

Company Confidential Information

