## 6.2 Secondary objectives

### 6.2.1 Variables

The secondary variables are the:

1. Body fat mass: change from baseline in fat mass after 6 months of treatment at Week 24
2. HbA1c: change from baseline will be used for inferential analysis at Week 24 and Week 48. Baseline for HbA1c is defined at the Day 1 assessment.
3. Fasting insulin and glucose at Week 12, Week 36, and EOS: Baseline for these parameters is defined at the Screening assessment.
4. HOMA2-IR: homeostatic assessment model of insulin resistance at Week 12, Week 36, and EOS
5. QUICKI: quantitative insulin sensitivity check, under fasting conditions at Week 12, Week 36, and EOS. QUICKI index will be derived from glucose and insulin levels at study completion using the following formula:

$$\text{QUICKI} = \frac{1}{\{\log(\text{Fasting Insulin}) + \log(\text{Fasting Glucose})\}}$$

6. Matsuda Index based on MTT at Week 24 and Week 48. Matsuda Index will be derived from glucose and insulin levels using the following formula:

$$\frac{10000}{\sqrt{(\text{Fasting Glucose} \times \text{Fasting Insulin}) \times (\text{Mean Glucose} \times \text{Mean Insulin})}}$$

7. Anthropometric body measurements: body weight, BMI, waist circumference, waist-to-hip ratio and lean body mass (LBM) as measured by DXA at Week 24 and Week 48.

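### In the public text the HbA1c model does not commit to adjusting for baseline HbA1c: its covariates are inherited from the fat-mass model and are optional

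*SAP*

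**What the plan says.** SAP 6.2.3 gives HbA1c one visible sentence of model specification: "The secondary analysis of HbA1c will be analyzed using a mixed effects model with the same structure as the analysis of the primary variable", with a pointer to SAP 6.1.3. A redacted block follows.

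SAP 6.1.3 describes that primary model. The outcome is change from baseline in fat mass, the fixed effects are treatment, categorical time and their interaction, and the within-subject covariance is unstructured. The covariate sentence begins "Baseline fat mass and baseline BMI value may". Protocol 11.4.2 has the same sentence in full: "Baseline fat mass and baseline BMI value may be included in the model as covariates". The protocol synopsis names the same two covariates for fat mass without the *may*.

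For the outcome itself, SAP 6.2.1 says "HbA1c: change from baseline will be used for inferential analysis at Week 24 and Week 48" and "Baseline for HbA1c is defined at the Day 1 assessment". So a baseline HbA1c value is defined, but in the visible text it serves only as the reference for the change score.

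The remaining secondary variables are covered by a sentence saying that an MMRM, similar to the HbA1c analysis, may be used.

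Two design facts bear on this. Protocol 4.1 admits patients with "Type 2 diabetes, with an HbA1c between 6.5% and 10% (inclusive) at screening". Protocol 6.5 says "Treatment is assigned by stratified randomization for two strata", and those strata are defined by baseline BMI alone.

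**The concern.** The cross-reference can be programmed in two ways. A literal programmer carries over baseline fat mass and BMI, and baseline HbA1c does not enter. Another treats baseline fat mass as the outcome's own baseline and substitutes Day 1 HbA1c, but inherits the *may*. Neither reading commits the analysis to adjusting for baseline HbA1c.

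HbA1c is the secondary endpoint for which Protocol 11.8 gives a pass rule (a significant reduction, and an estimated placebo-adjusted reduction of at least 0.5 points) together with power. The entry range spans 3.5 points at screening, and nothing in the randomisation balances HbA1c. If change in HbA1c depends on its starting value, leaving baseline out gives up some precision. It also leaves one analyst's choice able to move the estimate relative to the 0.5 threshold. Any such choice should be fixed before unblinding.

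**Working it through.** **Inputs.** True reduction 0.7, SD 1.11 and threshold 0.5 come from Protocol 11.8. The 24 completers per arm come from Protocol 11.7, and the 1-sided 10% level from Protocol 11.4.2, where it is stated for fat mass. Section 11.8 repeats neither the sample size nor the level, so both are carried over by assumption. It also does not say whether 1.11 is the SD of change; that too is assumed.

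**Step 1: reproduce the plan's figures with no covariate.**

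- SE = 1.11 × √(2/24) = 0.320.
- Significance alone needs an estimate of 1.2816 × 0.320 = 0.411. This is below 0.5, so the 0.5 threshold sets the cutoff.
- Power = Φ((0.7 − 0.5)/0.320) = 73.4% (stated: about 73%).
- Type I error = 1 − Φ(0.5/0.320) = 5.9% (Protocol 11.8: "The associated type I error is about 6" per cent).

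Both figures reproduce without adjustment. A 1-sided 5% level gives 70.5% and 5.0%, and 34 per arm gives 77.1% and 3.2%. Neither alternative matches the stated pair.

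**Step 2: add Day 1 HbA1c.** Let r be the correlation between baseline and follow-up HbA1c. With equal variances at the two times, the adjusted residual SD is 1.11 × √((1 + r)/2). The correlation of change with baseline is −√((1 − r)/2). The documents give no value for r, so a range is shown (normal approximation).

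| r | corr(change, baseline) | residual SD | SE | pass at true 0.7 | type I error |
|---|---|---|---|---|---|
| no adjustment | – | 1.11 | 0.320 | 73.4% | 5.9% |
| 0.4 | −0.55 | 0.929 | 0.268 | 77.2% | 3.1% |
| 0.7 | −0.39 | 1.023 | 0.295 | 75.1% | 4.5% |
| 0.9 | −0.22 | 1.082 | 0.312 | 73.9% | 5.5% |

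As the correlation of change with baseline goes to zero, the gain disappears.

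**Step 3: is the equal-variance assumption plausible?** It implies a baseline SD of 1.11/√(2(1 − r)), which is 1.01 at r = 0.4 and 1.43 at r = 0.7. A uniform spread over the 6.5 to 10 entry range has SD 3.5/√12 = 1.01. The upper end of the range is therefore strained, and the table is illustrative only.

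**Step 4: what the lost precision looks like in one trial.** Assume a baseline SD of 0.5 to 1.01. The SE of the between-arm baseline difference is then SD × √(2/24) = 0.14 to 0.29 points. With an assumed slope of change on baseline of −0.3 to −0.7, a one-SE imbalance moves the unadjusted estimate by 0.14 × 0.3 = 0.04 to 0.29 × 0.7 = 0.20 points, in either direction. The gap between the assumed effect and the threshold is 0.7 − 0.5 = 0.2. This variation is part of the unadjusted SE of 0.320, not an addition to it.

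**The case against.** The strongest objection is redaction. A blacked-out block follows the HbA1c sentence in SAP 6.2.3 and another follows the primary model in SAP 6.1.3. Protocol 11.5 and 11.5.1, on secondary efficacy analysis, are blacked out entirely. A covariate list could sit in any of them. A reader might infer that the plan never adjusts for baseline HbA1c. The documents do not support that; they show only that the visible text does not name it as a covariate. This objection stands, and it is why the redacted text must be checked first.

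Second, *same structure* need not mean the same variable list. The dependent variable is plainly meant to change, and baseline fat mass is the primary outcome's own baseline, so substituting Day 1 HbA1c is a natural reading. That is fair, but the substitution is not written down, and the substituted covariate would still be optional.

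Third, randomisation keeps the unadjusted comparison unbiased on average, and the stated operating characteristics already include chance imbalance. This stands. A reader who infers bias, or an error in the power statement, goes further than the documents allow.

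Fourth, nothing in the documents says that baseline HbA1c is the strongest predictor of HbA1c change. The predictor they name for HbA1c response is BMI (Protocol 3.2 and 6.5), which is already the stratification factor and a named covariate. The case for adjustment rests on general method and not on evidence in the plan.

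Fifth, the trial is described as non-confirmatory and the endpoint is secondary. This limits the weight of the point but does not remove it, since the remedy costs almost nothing.

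**Conclusion.** The point holds as a gap in pre-specification with a modest cost in precision. In the public text, baseline HbA1c is either outside the HbA1c model or optional in it, depending on how the cross-reference is read.

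At the assumed correlations of 0.4 to 0.7, the chance of passing rises by about 2 to 4 percentage points and the type I error of the rule falls by about 1.4 to 2.8 points. Both ranges depend on 1.11 being the SD of change, on equal variances, on 24 per arm, and on the 1-sided 10% level carrying over to HbA1c.

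The variance reduction corresponds to 1/0.85 = 1.18 to 1/0.70 = 1.43 times the sample size. A reader might infer from this that the trial is materially underpowered without adjustment. It is not: the 0.5 cutoff, and not the standard error, drives the decision, so the change in passing probability stays small.

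The wording for the other secondary variables commits to neither a model nor a covariate set. For them the point is a lack of specification, not a demonstrated omission.

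**What to change.** First check the redacted parts of SAP 6.1.3 and 6.2.3 and of Protocol 11.5 and 11.5.1. If they already make Day 1 HbA1c a required covariate, no change is needed for HbA1c.

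Otherwise add to SAP 6.2.3, before unblinding, text to this effect:

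> The HbA1c model will include Day 1 HbA1c and baseline BMI as covariates; Day 1 HbA1c takes the place of baseline fat mass. Any other secondary variable analysed by MMRM will include its own baseline value and baseline BMI. When BMI is the outcome, baseline BMI is entered once.

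The last sentence is needed because BMI is itself a secondary variable in SAP 6.2.1. Keeping baseline BMI in the model also reflects the stratification factor.

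The cost is two or three sentences in the SAP and about one degree of freedom. The HbA1c baseline is already collected on Day 1. No patient is lost by adjusting, because the change score cannot be formed without that same value.

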### **Other Secondary Variables**

Similar to the analysis of HbA1c, an MMRM model may be used to compare values between active and placebo groups for the remaining secondary variables.

#### **6.2.3.1 Supportive analyses**

As a supportive analysis for metabolic changes, summaries of change in background anti-diabetic medication may be done. A change in background anti-diabetic medication is defined as a change in daily dose, any discontinuation, or the addition of a second agent.

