Administration of bimagrumab or placebo will be done via an intravenous infusion over 30 minutes, followed by approximately 15 minutes for flushing and then an observation period that will include safety and tolerability and PK sampling. Following all assessments, subjects may be discharged from the Investigator site when the Investigator judges them to be medically stable, in good general health and not needing further observation.

Treatment period (Days 1 - 336)

Subjects should continue on anti-diabetes background therapy as per eligibility criteria (see [Section 4.1](#)) throughout the study. If, however, during the course of the study, a subject experiences an improvement or a deterioration of his/her glycemic control, modification of his/her background therapy can be made as defined in [Section 6.4](#) (Background therapy dose adjustments).

Administration of bimagrumab or placebo will be done via an intravenous infusion over 30 minutes followed by 10 to 20 minute observation period once every 4 weeks for a total of twelve doses. Bimagrumab will be dosed based on body weight at 10 mg/kg, with a dose cap of 1200 mg for body weight equal to and above 120 kg. Placebo will be provided by the site as 5% Dextrose solution (D5W) (see Pharmacy Manual for more details).

Subjects will receive regular monitoring and advice on diet and physical activity as part of their monthly site visits (please refer to [Section 8.1](#) (Assessment schedule)) throughout the study, and will be contacted by telephone, or scheduled for an in-person assessment, once between each monthly site visit to provide a 24-hour dietary recall. Additional methods for promoting weight loss may be incorporated into or used in place of standard clinical care; these methods may include the use of electronic tools for reporting dietary intake, weight or physical activity, and for receiving feedback on weight trends and lifestyle changes.

[figure not shown]
Subjects will be asked to return to the Investigator site for dosing approximately every 4 weeks during the treatment period. During these visits, subjects will be evaluated for safety, tolerability, PK and efficacy. The specific assessments for each of these visits are detailed in [Section 8.1](#) (Assessment schedule).

The treatment period will end approximately 4 weeks after the last dose administration.

Follow Up (Days 364 -392)

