3.5 Rationale for choice of background therapy

This trial in overweight or obese patients with T2D has the primary goal of assessing the effect of bimagrumab on body composition.

While improvement in glycemic control may occur as a result of improved body composition, subjects should maintain their background T2D therapy throughout to avoid deterioration in glycemic control. If, however, improvement in glycemic control is observed during the study, reduction in or discontinuation of anti-diabetic treatment is allowed under the guidance of a medical professional to prevent hypoglycemia as specified in [Section 6.4](#). T2D treatment is restricted to specific anti-diabetes therapy for homogeneity of the study population and to enable interpretability of the data. Anti-diabetes therapy is restricted to classes with minimal effect on body weight, including metformin, a first line therapeutic agent, and/or DPP4 inhibitors. Management of background therapy, including the potential need for managing worsening glycemic control, is presented in [Section 6.4](#).

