6.4 Background therapy dose adjustments

Adjustments of T2D background therapy are allowed, according to the standard of care, but are restricted to the following:

- Either increased or decreased dosage, or discontinuation, of current medication is allowed under the guidance of a medical professional;
- The add-on of a second medication is allowed but restricted to metformin or DPP4-inhibitor;
- Insulin, as an acute treatment for severe or uncontrolled hyperglycemia, such as during an acute illness, is allowed but restricted to one week only;

The Investigator must emphasize to the subjects the importance to communicate ANY change in the background medication. In particular, the Investigator must inform the subjects that ANY change in the anti-diabetes medication that IS NOT LISTED above, will cause the subject to discontinue study treatment. Any modification to the background therapy during study participation must be reported by the Investigator.

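### The SAP's definition of a change in anti-diabetic medication has no direction, so a by-arm summary built on it cannot separate reduced from intensified therapy

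*SAP*

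**What the plan says.** SAP 6.2.3.1 (Supportive analyses) says that "summaries of change in background anti-diabetic medication may be done", as support for interpreting metabolic changes. It then defines the event: "A change in background anti-diabetic medication is defined as a change in daily dose, any discontinuation, or the addition of a second agent". The visible text does not split the event by direction.

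The protocol lets therapy move both ways:

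- Section 3.1 (Treatment period): if "a subject experiences an improvement or a deterioration of his/her glycemic control, modification of his/her background therapy can be made".
- Section 3.5: when control improves, "reduction in or discontinuation of anti-diabetic treatment is allowed under the guidance of a medical professional to prevent hypoglycemia".
- Section 6.4: "Either increased or decreased dosage, or discontinuation, of current medication is allowed under the guidance of a medical professional", and "The add-on of a second medication is allowed but restricted to metformin or DPP4-inhibitor".

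SAP 6.2.3 gives HbA1c the same model structure as the primary endpoint. The visible text has no term or rule for medication changes. SAP 7.2 and Protocol 11.3 provide listings of concomitant therapies by group and subject. The sentence in SAP 6.2.3.1 is therefore the only visible arm-level summary of background diabetes therapy.

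**The concern.** The summary is there to help interpret metabolic results, yet the event it counts has no metabolic sign. A subject whose metformin is lowered after improvement and one whose metformin is raised after deterioration both have a change.

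This matters most if bimagrumab works. Reductions would then be expected to collect on bimagrumab and intensifications on placebo, and both narrow the HbA1c difference between arms. A reader of the HbA1c result needs to know whether that happened. A similar proportion with any change in each arm could be taken as reassurance when the two arms had moved in opposite directions.

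**Working it through.** **The plan's own HbA1c figure.** Protocol 11.8 assumes a placebo-adjusted reduction of 0.7 with SD 1.11, and requires significance plus an estimate of at least 0.5. Protocol 11.7 gives 24 completers per arm. The significance level for HbA1c is not stated; I assume the 1-sided 10% used for fat mass.

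- SE = 1.11 × √(2/24) = 0.320
- Significance cut = 1.282 × 0.320 = 0.411, below 0.5, so the 0.5 threshold binds
- Power = 1 − Φ((0.5 − 0.7)/0.320) = 73.4% (stated: about 73%)
- Type I error = 1 − Φ(0.5/0.320) = 5.9% (stated: about 6%)

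The figures reproduce. No medication variable enters them, so the wording of SAP 6.2.3.1 cannot alter them.

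**The definition applied to four permitted events.**

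| Event | Direction | Under SAP 6.2.3.1 |
|---|---|---|
| Daily dose lowered | reduced | change |
| Daily dose raised | intensified | change |
| Agent stopped, not replaced | reduced | change |
| Second agent added | intensified | change |

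This step needs no assumed rate: the classification alone removes the sign.

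**What a by-arm count of the event shows.** Let r and i be the proportions reduced and intensified, with each subject in at most one category, and let Δ be bimagrumab minus placebo. The difference in any change is Δr + Δi. The net shift towards less therapy on bimagrumab is Δr − Δi. The count therefore reports a sum when the two parts are needed separately.

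The documents give no rates, so all rates below are assumptions.

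| Case | Bimagrumab r / i | Placebo r / i | Any change | Difference, any change (points) | Δr (points) | Δi (points) | Net shift (points) |
|---|---|---|---|---|---|---|---|
| A | 20% / 5% | 5% / 20% | 25% v 25% | 0 | +15 | −15 | +30 |
| B | 20% / 5% | 5% / 30% | 25% v 35% | −10 | +15 | −25 | +40 |
| C | 30% / 5% | 5% / 20% | 35% v 25% | +10 | +25 | −15 | +40 |
| D | 5% / 5% | 5% / 30% | 10% v 35% | −25 | 0 | −25 | +25 |
| E | 5% / 20% | 20% / 5% | 25% v 25% | 0 | −15 | +15 | −30 |

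- A and E give the same any-change result with opposite meanings.
- B and C have the same net shift, but their any-change differences have opposite signs.
- In D, where reductions are equal across arms, nothing is masked: the any-change difference equals the intensification difference.

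Offsetting is therefore complete in A and E, partial in B and C, and absent in D.

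**Why direction bears on HbA1c.** Suppose one step of therapy moves HbA1c by e points, the same for reductions and intensifications. The therapy changes then alter the between-arm difference by about net shift × e. In case A, the 0.2-point gap between the assumed 0.7 and the 0.5 criterion is used up when e = 0.2/0.30 = 0.67. In case E the same arithmetic exaggerates the difference instead of diluting it. The documents give no value for e. This shows only that direction matters; it does not estimate the dilution.

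**The case against.** The strongest reply is that the SAP sentence lists qualifying events and does not prescribe a pooled count. It allows summaries in the plural, and a table by type of change would fit the wording. That is fair, and such a table would separate add-ons from discontinuations. But it is permitted and not required, and dose changes would still be undirected within their own row.

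Several further points stand as limits:

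- A reader might infer that improvement in one arm and deterioration in the other necessarily cancel. The documents do not support that. Cancellation depends on rates they do not give, and it is complete only when the rates mirror each other.
- A reader might also infer that this definition costs HbA1c effect or power. It does not. Any dilution comes from the therapy changes that Protocol 6.4 permits, and a better table would leave the estimate, the criterion and the power as they are.
- The summary is optional, descriptive and attached to a secondary endpoint in a non-confirmatory study. The primary fat-mass analysis is untouched.
- Direction remains in the data. Protocol 6.4 requires any modification to be reported, and subject listings are planned. A determined reader could reconstruct it, but no arm-level figure is provided.
- Direction is not cause. A dose may be reduced or an agent stopped for reasons other than improvement, so a directional table also needs careful labelling.
- Protocol 11.5.1 and the text after the HbA1c model in SAP 6.2.3 are blacked out, and SAP 1.1 points to further reporting documents. The absence of a split can be asserted only for the visible text.

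**Conclusion.** The point holds in a limited form. As written, the definition treats therapy moves of opposite meaning as one event, and a by-arm summary of that event cannot serve the purpose SAP 6.2.3.1 gives it. This follows from the text alone.

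The size is illustrative only. Under mirrored rates of 20% and 5%, the any-change difference is 0 points while each direction differs by 15. Under unequal rates the offset is partial, and with equal reductions in the two arms there is none.

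The loss is in interpretation. Readers would have no arm-level view of whether background therapy moved so as to dilute, or exaggerate, the HbA1c difference. No estimate, criterion or stated power is affected.

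**What to change.** In SAP 6.2.3.1, replace the single definition with three categories:

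- **Reduced:** lower daily dose, or an agent stopped without replacement.
- **Intensified:** higher daily dose, or an agent added.
- **Mixed or switched:** both.

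Tabulate the number and percentage in each category by arm at Week 24 and Week 48, with the between-arm differences in reduced and in intensified, and place the table beside the HbA1c result. Label the categories as direction of change, not as improvement or deterioration.

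The cost is one revised definition and one table. Protocol 6.12 already has dose, frequency and start and stop dates recorded for each medication, so no new data are needed. The drawback is sparse cells: with about 34 per arm, 5% is fewer than two subjects (0.05 × 34 = 1.7). The table should therefore be read as counts and not tested.
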